1.4.2 Secondary Efficacy Objectives

1.4.2.1 *Battery Life*

The secondary efficacy endpoint for battery life will be based on battery logs as recorded by the subject during the take-home period with each strategy. The objective of this secondary endpoint is to demonstrate superiority of FAST compared to ACE for battery life. Success for this secondary endpoint will be based on rejection of the null hypothesis that battery life with FAST is less than or equal to battery life with ACE. The estimated within-subject mean difference in battery life between FAST and ACE will be reported with a 95% confidence interval. A one-sided t-test will be conducted at the 0.025 significance level. The secondary endpoint for difference in battery life is represented by the following hypotheses:

$$H_0: BLD \leq 0,$$

$$H_a: BLD > 0,$$

where:

BLD = within-subject battery life difference for FAST – ACE.

1.4.2.2 *Speech, Spatial, and Qualities of Hearing Scale (SSQ12-C)*

The secondary efficacy endpoint for the quality and speech understanding questionnaire will be based on subjects' responses on the SSQ12-C as recorded one month after crossover from the first strategy to the second strategy. The SSQ12-C is a comparative, closed-ended questionnaire composed of 12 items assessing speech perception, spatial hearing, sound quality, and listening effort. A response of 0 on the questionnaire indicates equivalent performance between FAST and ACE, while positive or negative responses indicate a preference for one strategy over the other.

The difference between the two study groups will be evaluated with a two-sided t-test using average responses on the SSQ12-C across the 12 questions within each group. Success for this secondary endpoint will be based on a non-significant result, indicating no difference between the two groups in terms of crossing over from one strategy to the other (i.e., not rejecting the null hypothesis that responses from the two groups are equivalent). The mathematical expressions are:

$$H_0: \mu_{G1} = \mu_{G2},$$

$$H_a: \mu_{G1} \neq \mu_{G2},$$

where:

μ_{G1} = mean response value on the SSQ12-C for Group 1;

μ_{G2} = mean response value on the SSQ12-C for Group 2.

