2.0 Study Objectives

Primary Objectives:

1. To determine if FAST is non-inferior to ACE for word recognition in quiet in newly-implanted cochlear-implant recipients.
2. To determine if FAST is non-inferior to ACE for sentence perception in noise in newly-implanted cochlear-implant recipients.

Primary Endpoints:

1. Word recognition in quiet will be non-inferior for FAST compared to ACE.
2. Sentence perception in noise will be non-inferior for FAST compared to ACE.

Secondary Objectives:

1. To quantify the battery life benefit for FAST compared to ACE.

CONFIDENTIAL

2. To obtain insight into sound quality differences between the strategies and the relative difficulty of conversion for the cochlear-implant recipient from ACE to FAST versus FAST to ACE.

Secondary Endpoints:

1. Duration of battery life will be superior for FAST compared to ACE.
2. Comparative ratings on a hearing questionnaire will not be significantly different between the two experimental groups.

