5.0 Investigational Procedures

5.1 Design Overview

This study will implement a within-subject crossover design with 20 subjects. All subjects will receive each of the treatments – the ACE and FAST strategies. In this repeated measures design, half of the subjects, Group 1, will be mapped with FAST first and the other subjects, Group 2, with ACE first, using formalized mapping procedures. Endpoint speech perception testing, additional to standard clinical testing, will be conducted after 3 months of use with the initial strategy. At the 3-month post initial activation (IA) session, each recipient will be programmed with the crossover strategy. The crossover strategy will then be assessed after 3 months of take-home use at 6 months post IA (refer to Table 1). As indicated in Table 1, fine-tuning of the cochlear implant stimulation levels (i.e. MAP) will occur at 1 week and 1 month after receiving each strategy. Standard clinical testing will also occur at 3 months and 6 months post activation.

The order in which the subjects are programmed with the ACE and FAST strategies will be counterbalanced according to group; Group 1 will start with FAST and Group 2 with ACE. Subjects will be randomly assigned to either Group 1 or 2. Standardized programming procedures will be used to program the FAST and ACE strategies. Subjects will be blinded as to the identity of the strategies.

The study design strikes a balance between providing a reasonable amount of take-home experience with each of the strategies and obtaining outcome comparison data for the strategies within the required timeframe. It is acknowledged that maturational effects are not eliminated with crossover to the alternative strategy at 3 months post IA. The exclusion criteria for enrollment will provide control over some of these variables. To further address maturational effects, subjects' scores from the Reading Span Test (a cognitive test of working

CONFIDENTIAL

memory) will be included as a statistical covariate to understand differences in adaptation that might be associated with working memory.

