Depending on the Clinical Site, endpoint speech perception evaluations will be conducted either at the Clinical Site or at the Denver Research & Technology Labs (Cochlear Americas). These evaluations will include sentence in noise testing in dynamic four-talker babble and speech-shaped noise. The test setup will be with the target speech and competing noise both presented from a speaker in front of the recipient (S0N0). A speech reception threshold (SRT) will be obtained, which represents the signal-to-noise ratio (SNR) at which the recipient scores 50% intelligibility. Word recognition in quiet will also be conducted.

All subjects will be implanted with a CI24RE, CI512, or CI532 implant and will be given the latest commercially available sound processor. However, recipients will be fit with a CP810 sound processor with no advanced features for the duration of the study (adaptive directionality, wireless accessories, and SmartSound iQ will not be used during study participation).

At the crossover appointment (3 months post IA), endpoint speech perception testing will be conducted with the first strategy. The second strategy will then be programmed for take-home use. Subjects will be asked to acutely rate sound quality with this second strategy in direct comparison to the first strategy. One month after take-home use with the second strategy, subjects will be asked to complete a questionnaire again rating sound quality and speech understanding with the second strategy compared to the first strategy. Comparing the quality of strategy 2 to strategy 1 after a longer period of take-home use with strategy 2 is likely to be less reliable, given reliance on the memory of strategy 1.

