Evaluating the sound quality of FAST versus ACE is complex. To minimize memory effects and increase statistical power, a direct comparison of strategies would be ideal. The comparative quality ratings of ACE and FAST at the crossover appointment will provide some insight into sound quality with the two strategies. If the conversion from the initial strategy to the crossover strategy shows larger quality differences for one of the two groups, this may indicate underlying disparities between the two strategies. However, based on previous research with existing recipients, it is known that the sound quality of FAST differs from ACE. The quality and speech understanding questionnaire conducted one month after the crossover appointment will provide further understanding of quality differences after some degree of acclimatization.

Subjects in Group 2 who are initially programmed with ACE and then reprogrammed with FAST at the crossover 3 months post IA will need to be re-programmed with the default ACE program at the final visit 6 months post IA. The ACE map will be fine-tuned at this final visit and will be loaded onto the patient's

CONFIDENTIAL

IDE #G150140 V2.4 September 28, 2017

Page 12 of 24

CAM-CL-111_F

Rev. 1

personal sound processor for take-home use. Instruction will be provided on the use of the processor controls.

The FAST strategy is not currently approved by the FDA as a commercial speech processing strategy that recipients may choose as their clinical strategy for ongoing use. Subjects will be informed prior to enrolling that they will not have the option of continuing to use FAST after the completion of this study. However, this study may provide data for a future submission to seek FDA approval for FAST. In the event that the FAST strategy becomes clinically approved in the future, the current subjects will have access to FAST through their clinical audiologists. At the conclusion of the study, subjects will be provided with the option to upgrade to a compatible sound processor. This option must be redeemed within 5 years from completion of the study.

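### The SSQ12-C group comparison mixes strategy preference with conversion difficulty, so a non-significant result cannot be read as equal ease of crossing over

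*Combined protocol and SAP*

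**What the plan says.** Secondary objective 2 (protocol 2.0 and synopsis) has two parts. One is to learn how FAST and ACE differ in sound quality; the other concerns "the relative difficulty of conversion for the cochlear-implant recipient from ACE to FAST versus FAST to ACE". The SSQ12-C is the secondary endpoint attached to it.

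- **Order.** Under protocol 5.1, "half of the subjects, Group 1, will be mapped with FAST first and the other subjects, Group 2, with ACE first".
- **What is rated.** One month after the switch, "subjects will be asked to complete a questionnaire again rating sound quality and speech understanding with the second strategy compared to the first strategy" (protocol 5.1). Group 1 therefore rates ACE against FAST, and Group 2 rates FAST against ACE. Protocol 5.2.7 and Table 1 show a single administration, at 4 months post activation.
- **What a response means.** SAP 1.4.2.2 treats 0 as equivalence and says that "positive or negative responses indicate a preference for one strategy over the other". It does not fix which strategy a positive score favours.
- **Test and reading.** The group means are compared with a two-sided t-test. Success is a non-significant result (SAP 1.5 gives the 0.05 level), which SAP 1.4.2.2 interprets as "indicating no difference between the two groups in terms of crossing over from one strategy to the other".

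**The concern.** SAP 1.4.2.2 describes the individual response as a preference between strategies and then describes the comparison of mean responses as a statement about conversion. No step leads from the first to the second. Because the groups rate in opposite directions, a lasting preference for either strategy pushes their means apart even when the switch is equally easy both ways.

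At stake is what the trial may conclude about conversion. Difficulty in moving from ACE to FAST is part of the study's rationale (protocol 1.0) and a named risk (protocol 9.2). The plan attaches a formal success rule and a conversion claim to a quantity that does not measure conversion. More subjects, or a formal equivalence margin, would only estimate the same mixture more precisely.

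**Working it through.** The documents state no SD, power, margin or sample size for the SSQ12-C, so there is no plan figure to reproduce. The stated minimum sizes of 8 and 11 belong to the co-primary endpoints.

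**Notation**, in SSQ12-C scale points (a simple additive model):
- d: lasting preference for FAST over ACE
- g: gain from maturation, shared by both groups (protocol 5.1 accepts that maturation continues past the crossover)
- cF, cA: penalties still present at one month for converting into FAST and into ACE

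**Scored as second minus first strategy** (the direction in protocol 5.1):
- Group 1 (FAST then ACE): mean = g - d - cA
- Group 2 (ACE then FAST): mean = g + d - cF
- G2 - G1 = 2d - (cF - cA)

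The contrast equals (minus) the conversion difference only if d = 0.

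**Scored as FAST minus ACE** (possible, since the SAP gives no direction):
- Group 1 changes sign: mean = -g + d + cA
- Group 2 is unchanged: mean = g + d - cF
- G2 - G1 = 2g - cF - cA

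Preference now cancels, but what remains is maturation less the sum of the penalties, not their difference.

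**Estimability.** There are two group means and four unknowns. The coefficient matrix of the means has rank 2. Adding the row for cF - cA raises it to 3, so cF - cA cannot be estimated from these data.

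**Illustrations** (second minus first; the values are assumptions):
- d = +0.5, cF = 1.0, cA = 0: contrast = 2(0.5) - 1.0 = 0. Conversion to FAST is a full point harder, yet the test passes 95% of the time whatever the SD.
- d = -0.75, cF = cA: contrast = 2(-0.75) = -1.5. Conversion is equally easy, yet the contrast is not zero. With d = +0.75 it is +1.5, and the two-sided test treats it the same way.

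**Pass probability for a 1.5-point contrast.** Two-sample t-test, 10 per group, two-sided 0.05, df = 18, critical value 2.101, noncentrality = (1.5/SD) × √(10/2):

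| Assumed SD | Noncentrality | P(non-significant) |
|---|---|---|
| 1.0 | 3.35 | 11% |
| 1.5 | 2.24 | 44% |
| 2.0 | 1.68 | 65% |
| 2.5 | 1.34 | 75% |

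**Same result from different causes.** In SD units, a preference against FAST of 0.5 with equal conversion gives a contrast of size 2(0.5) = 1. So does no preference with conversion to FAST 1 SD harder. Both pass 44% of the time, and the test cannot tell them apart.

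**The case against.** Four points can be made for the plan.

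1. **The objective is modest and has other sources.** It seeks only insight, acute quality ratings are also taken at crossover (protocol 5.2.3), and the protocol endpoint says only that ratings will not differ significantly between groups. Protocol 5.1 already reads a group difference in the acute ratings as a possible disparity between strategies, and presents the one-month questionnaire as informing quality differences. This stands, and it confines the fault to the inference in SAP 1.4.2.2. It does not rescue that inference; the protocol's own reading sits better with a strategy effect.

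2. **No signed preference is established.** A reader might infer from "it is known that the sound quality of FAST differs from ACE" that d is known to be non-zero in this trial. The documents do not support that: the sentence rests on research in existing recipients, and a difference in quality is not a preference. What stands is narrower. The SAP's reading needs d = 0, and nothing in the documents justifies assuming it.

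3. **The magnitudes are assumed.** A reader might infer that the endpoint will usually mislead. That is unsupported too. The hidden-asymmetry example needs a preference for FAST that offsets harder conversion to FAST. If both ran against FAST they would add, and the test would tend to fail. The 1.5-point contrast fails more often than not at an SD of 1 or 1.5, and passes more often than not at 2 or 2.5.

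4. **The endpoint does not drive study success.** SAP 1.5 defines success by the two co-primary endpoints alone. This stands in full.

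**Conclusion.** The SSQ12-C contrast does not measure relative difficulty of conversion under either scoring direction, and the crossing-over conclusion in SAP 1.4.2.2 should not be drawn from a pass or a fail. Under the direction in protocol 5.1, each point of preference enters with weight 2 and each point of conversion asymmetry with weight 1. This rests on the additive model, a maturation gain common to both groups, and a single rating per subject; it needs no particular effect size. How often a wrong conclusion would result cannot be determined from the documents.

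The contrast is still usable as a net comparison of the strategies one month after the switch, which serves the sound-quality half of secondary objective 2. The point is separate from whether non-significance is an acceptable success criterion. It is worth correcting because the plan would otherwise license a conclusion that its data cannot support.

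**What to change.** In SAP 1.4.2.2:

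- Define the score as second minus first strategy, matching protocol 5.1.
- Report (G2 - G1)/2 = d - (cF - cA)/2 with its 95% CI, labelled as the net FAST-over-ACE rating one month after the switch, preference and conversion combined. With 10 per group, the half-width is 2.101 × SD × √(2/10) / 2, about 0.47 SD.
- Delete the inference about crossing over.
- State that the endpoint addresses the sound-quality part of secondary objective 2 and does not separately estimate relative conversion difficulty.

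The cost is wording; no data collection changes.

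Repeating the four crossover ratings at Visit 7 and comparing the change between groups is not recommended as a measure of conversion difficulty. A stable preference would cancel, but so would any penalty that persists over the month. With cF = 1.0 and cA = 0 at both visits, the change contrast is 0. Persistence is plausible: protocol 9.2 reports that some experienced ACE users had trouble adapting to FAST across 18 weeks. The repeat would also add an assessment and need a protocol amendment.

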1.5 Type I Error Control

Study success will be defined by rejection of the null hypotheses of inferiority of FAST compared to ACE for both of the two co-primary endpoints. Because study success depends on the two endpoints together, type I error will be maintained at an overall one-sided alpha level of 0.025.

Secondary efficacy analyses will be conducted using two additional variables: battery life duration and the SSQ12-C. Success for the battery life endpoint will be based on rejection of the null hypothesis that FAST is not superior to ACE at a one-sided alpha level of 0.025. However, success for the SSQ12-C analysis will be based on a non-significant result at the 0.05 level for a two-sided test, indicating no significant difference. Therefore, adjustments for multiplicity will not be made for the secondary efficacy analyses, as such adjustments would actually increase the chance of finding no significant difference and thus increase the possibility for incorrectly passing the SSQ endpoint.

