1.4.1 Primary Efficacy Objectives

The two co-primary efficacy endpoints will be based on analyses of CNC word recognition and BKB sentence reception in babble and speech-shaped noise after 3 months of experience with each strategy (collected at 3-months and 6-months post initial activation). The objective of the two co-primary efficacy endpoints is to test for non-inferiority of FAST compared to ACE. Study success will be defined by rejection of the null hypotheses for both of the two co-primary endpoints.

1.4.1.1 *First Co-Primary Efficacy Endpoint: CNC Word Recognition*

The objective of the first co-primary efficacy analysis is to demonstrate non-inferiority of FAST compared to ACE for word recognition in quiet as evaluated with the CNC test. Success for the first co-primary endpoint will be based on rejection of the null hypothesis of inferiority, with a non-inferiority margin of 10 rau based on clinical judgment and variability observed in previous studies ($M_2 = 10$). The treatment effect will be estimated using a LMM adjusted for period and sequence and a random effect for subject. If the upper 97.5% confidence bound is less than 10 rau, statistical significance will be met at the 0.025 alpha level. The first co-primary endpoint is represented by the following hypotheses:

$$H_0: CNC_{diff} \geq 10 \text{ rau},$$

$$H_a: CNC_{diff} < 10 \text{ rau},$$

where:

CNC_{diff} = ACE – FAST treatment difference, controlling for period and sequence effects, for CNC word recognition in rationalized arcsine units (rau).

1.4.1.2 *Second Co-Primary Efficacy Endpoint: BKB Sentence Reception in Noise*

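### Battery-life superiority is declared at its own one-sided 0.025, whatever the co-primaries show, and the reason given for leaving it unadjusted fits only the SSQ12-C

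*Combined protocol and SAP*

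**What the plan says.** **Co-primaries.** SAP 1.4.1 sets the study-level rule: "Study success will be defined by rejection of the null hypotheses for both of the two co-primary endpoints". SAP 1.5 concludes from it that "type I error will be maintained at an overall one-sided alpha level of 0.025".

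**Battery life.** SAP 1.4.2.1 gives this endpoint its own success criterion: "Success for this secondary endpoint will be based on rejection of the null hypothesis that battery life with FAST is less than or equal to" that with ACE. On the level it says "A one-sided t-test will be conducted at the 0.025 significance level". The estimated within-subject difference is reported with a 95% confidence interval. SAP 1.5 repeats the criterion: "Success for the battery life endpoint will be based on rejection of the null hypothesis that FAST is not superior to ACE".

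**SSQ12-C.** Success is a non-significant two-sided test at 0.05 (SAP 1.4.2.2 and 1.5).

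**Multiplicity.** SAP 1.5 says that "adjustments for multiplicity will not be made for the secondary efficacy analyses, as such adjustments would actually increase the chance of finding no significant difference". The only reason offered is that adjusting would "increase the possibility for incorrectly passing the SSQ endpoint".

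Neither the SAP nor the protocol orders the tests or makes the battery test depend on the co-primary results.

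**The concern.** One decision is applied to two secondary endpoints that work in opposite directions. For the SSQ12-C, a stricter level makes significance harder to reach and so makes success easier; declining to adjust is reasonable there. For battery life, a stricter level or a precondition makes a false success less likely. The two tests are separate, so protecting battery life need not touch the SSQ12-C level. The SAP therefore gives no applicable reason for leaving battery life outside any error control.

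What is at stake is the set of claims the study may make. Battery superiority is a named secondary endpoint (protocol 2.0), low power use is the first attraction of FAST given in protocol 1.0, and protocol 5.1 says the data may feed a later FDA submission. The plan as written allows a declared battery success next to a speech result that missed its margin. That outcome is foreseeable: protocol 1.0 says slow acclimatization made non-inferiority hard to show in experienced recipients, and protocol 9.2 says some of them struggled over 18 weeks. The study enrols new recipients to reduce this difficulty, but each of them must still convert once.

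**Working it through.** **Inputs from the documents**
- Co-primaries: one-sided 0.025 each, both required (SAP 1.4.1, 1.5).
- Battery life: one-sided 0.025, unconditional (SAP 1.4.2.1, 1.5).
- CNC: margin 10 rau, SD 7.20 rau, 8 subjects for 90% power. BKB: margin -2 dB, SD 1.84 dB, 11 subjects. Planned enrolment 20 (SAP 1.2, protocol 8.2).

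**Assumptions not in the documents**
- The correlation between the battery and co-primary statistics is not given, so a range is shown.
- The true battery benefit is not given; the false-claim figures for battery life take it as zero.

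**Step 1: the plan's own figures.** When both tests must pass, the largest chance of false study success is reached with one endpoint exactly at its margin and the other passing almost surely: 0.025 x 1 = 0.025. This agrees with SAP 1.5. The sample sizes also reproduce with a paired noncentral t at one-sided 0.025 and a true difference of 0: CNC with 8 subjects has power 91.8% (86.2% with 7); BKB with 11 has 90.0% (86.3% with 10). With 20 subjects the powers are above 99.9% and 99.6%, so a co-primary with no true difference is indeed almost sure to pass under the plan's assumptions.

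**Step 2: add the battery claim.** Let p be the chance of false study success and 0.025 the chance of a false battery claim. Under independence, the chance of at least one false claim is 1 - (1 - p)(1 - 0.025).

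| Situation, no true battery benefit | Chance of at least one false claim |
|---|---|
| One co-primary at its margin, other sure to pass (p = 0.025) | 1 - 0.975^2 = 4.94% |
| CNC at its margin, BKB with power 99.6% (p = 0.025 x 0.996) | 4.93% |
| Both co-primaries at their margins and independent (p = 0.025^2) | 1 - 0.999375 x 0.975 = 2.56% |
| Upper bound under any dependence | 0.025 + 0.025 = 5.0% |

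**Step 3: dependence.** Taking the first row and a bivariate normal for the two statistics, the rate is 4.8% at correlation 0.3, 4.5% at 0.5, 4.4% at 0.6 and 3.9% at 0.8.

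**Step 4: if a battery benefit exists.** Rejecting the battery null is then correct. The only possible false claim is study success, so the rate is at most 2.5% with or without a gate.

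**Step 5: with a gate.** Suppose battery life is tested only after both co-primary nulls are rejected. If a co-primary null is true, any false claim requires that null to be rejected, which has probability at most 0.025. If neither is true, the only possible false claim is the battery claim, again at most 0.025. The rate is held at 2.5% under any correlation.

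**Step 6: the split result.** If study success has false-claim probability 0.025 and there is no battery benefit, a false battery success beside a failed study has probability 0.025 x 0.975 = 2.4% under independence. When the battery benefit is real the split result involves no false battery claim, but it can still occur.

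**The case against.** The case for leaving the plan alone has real substance.

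- **The 0.025 statement is not an error.** A reader might infer that SAP 1.5 misstates its type I error and that the true figure is 4.9%. The documents do not support that. Study success is defined by the co-primaries alone, the 0.025 refers to it, and the lack of adjustment for the secondaries is disclosed. A battery result cannot turn a failed study into a success. This stands.
- **Only one secondary endpoint claims success by rejection.** Within the secondary family the error for a superiority claim is already 0.025. Control across primary and secondary endpoints is needed only if battery life is to be a confirmatory claim. Protocol 5.1 says no more than that the data may support a submission, protocol 9.1 speaks of informing later development, and the battery objective in protocol 2.0 is to quantify the benefit. This lowers the weight but does not remove the point, because protocol 2.0 and SAP 1.4.2.1 also name superiority as the endpoint, with a declared success.
- **The 4.9% needs several conditions at once, including no battery benefit.** The protocol expects a benefit, and any benefit brings the rate to 2.5% or less. This stands: the figure is a near-worst case and should be labelled so.
- **A battery result may be worth knowing even when speech fails.** A reader might infer that such a result is meaningless. Nothing in the documents says so, and power use can be informative when a 20-subject non-inferiority test narrowly misses. The gate concerns the formal claim; the estimate and interval are reported either way.

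None of this supplies a reason for exempting battery life. The one the SAP gives points the wrong way for a superiority test.

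**Conclusion.** The point holds as a gap in the testing hierarchy and a misapplied reason. The rate of false co-primary or battery claims is about 4.9% without a gate only in the near-worst case set out above, under independence and with no true battery benefit; under the other assumptions examined it runs from there down to 2.5% or below. With a gate it is 2.5% throughout. If the battery benefit is real, as the protocol expects, the gain is not in the error rate but in settling beforehand what may be claimed when a co-primary fails. The figures cover the co-primary and battery claims only. A wrong SSQ12-C pass is a missed difference, a different kind of error, and lies outside them. The primary conclusion is unaffected.

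**What to change.** Amend two places in the SAP, so that they do not contradict each other.

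**SAP 1.5.** Replace the joint statement on the secondaries with text to this effect: *The battery-life null is tested at one-sided 0.025 only when both co-primary nulls have been rejected. If either is retained, the FAST - ACE difference and its 95% confidence interval are given descriptively, and no success is declared. The SSQ12-C lies outside this sequence and stays at two-sided 0.05 without adjustment, because a stricter level would make its criterion easier to meet.* This keeps the existing rationale and confines it to the endpoint it fits.

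**SAP 1.4.2.1.** Add the same condition to the success criterion.

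The cost is a few sentences. Sample size, visits, test statistics and the SSQ12-C level do not change, and power for battery life is unchanged whenever both co-primaries succeed. The downside is that no formal battery-superiority claim can be made if either co-primary fails. An SSQ12-C success could still stand beside a failed speech result; this change does not address that.
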